#### 9.5.4. Bone Age

The change from baseline to Week 28 in the ratio of bone age to chronological age (BA:CA) is a secondary endpoint in the subgroup of subjects not at adult height (female subjects with the most recent prior bone age <14 years and males with the most recent prior bone age <16 years at study entry) and not on gonadotropin-releasing hormone agonist therapy, growth hormone therapy, or aromatase inhibitors at study entry. BA:CA will be calculated at baseline and Week 28 by taking the bone age of the subject and dividing it by the chronological age of the subject at each respective visit. The change from baseline to Week 28 in BA:CA will be analyzed using an ANCOVA model, as described in Section 9.2.1. Descriptive statistics and LS means for change

from baseline to Week 28 in BA:CA will be presented by treatment group along with the LS-mean treatment difference, 95% confidence intervals, and p-value.

The change from baseline to Week 28 in the difference in bone age and chronological age (BA-CA) will also be analyzed using an ANCOVA model, as described in Section 9.2.1. Descriptive statistics and LS means for change from baseline to Week 28 in BA-CA will be presented by treatment group along with the LS-mean treatment difference, 95% confidence intervals, and p-value.

# 9.6. Exploratory Efficacy Endpoints

The following sections describe the exploratory efficacy endpoints and methods of summarization and analysis. For all analyses of the exploratory efficacy endpoints, missing data will not be imputed and only observed cases will be used. All p-values produced from the analyses in this section will be considered nominal p-values and will not be adjusted for multiplicity.

### 9.6.1. Serum or Plasma Hormone Measurements

Serum or plasma hormone measurements including ACTH, testosterone, FSH, LH, and cortisol will be summarized with descriptive statistics by visit and treatment group. For hormones and visits where more than one sample is collected, the average of the visit values will be analyzed. For hormones or visits where more than one pre-morning GC dose sample is collected, the average of the pre-morning GC dose will be analyzed; otherwise, the pre-morning GC dose result is the single value collected. Observed and change from timepoint-matched baseline values will be summarized for visit average values and pre-morning GC dose values. Summaries of testosterone, LH, and FSH will be stratified by sex and Tanner stage (breast or testicular Tanner stages 1, 2 vs. Tanner stages 3-5).

The change from baseline to Week 28 for each of these parameters will be analyzed using an ANCOVA model as described in Section 9.2.1. Descriptive statistics and LS means for change from baseline to Week 28 in each of these hormone parameters will be presented by treatment group along with the LS-mean treatment difference, 95% confidence intervals, and p-value.

Mean (±SEM) values of serum hormone parameters at each visit will be summarized in line graphs by treatment group. Pre-morning GC dose values and visit average values will be presented on separate plots. Similar graphs will be presented for the changes from baseline.

A responder definition for the normalization of testosterone in female subjects will be defined as female subjects with testosterone levels that are greater than or equal to 1.2x ULN (based on age) at baseline and decrease to within the normal range at Week 28. The number and percentage of female subjects meeting this responder definition at Week 28 will be summarized by treatment group.

A responder definition for the ratio of androstenedione to testosterone (A4/T) in male subjects (Tanner stage 2 [testicular] and above) will be defined as male subjects who have A4/T greater than or equal to 0.5 (based on the pre-glucocorticoid dose values for androstenedione and testosterone) at baseline and who achieve A4/T less than 0.5 at Week 28. The number and percentage of male subjects meeting this responder definition at Week 28 will be summarized by treatment group.

The achievement of response for testosterone in female subjects and A4/T in male subjects at Week 28 (as defined for each of the responder analyses described above) will be analyzed using a CMH test as described in Section 9.2.2. The CMH test will compare treatment groups and will include stratification factors used in the randomization (with the exception of sex). Subjects who are missing Week 28 data will be omitted from the analysis.

### 9.6.2. Salivary Hormone Measurements

Salivary hormone measurements, including androstenedione, testosterone, cortisol, progesterone, and pregnenolone will be summarized with descriptive statistics by timepoint and treatment group. Summaries of testosterone, progesterone, and pregnenolone will be stratified by sex and Tanner stage (breast or testicular Tanner stages 1, 2 vs. Tanner stages 3-5). For visits where more than one pre-dose sample is collected, the average of the pre-dose values will be analyzed. Otherwise, the pre-dose result is the single value collected. For visits where more than one sample is collected, the average of all timepoints at that visit will be averaged and analyzed as the mean 24-hour value. Observed and change from timepoint-matched baseline will be summarized for pre-dose values and mean 24-hour values.

The change from baseline to Week 28 in mean 24-hour values for each of the parameters will be analyzed using an ANCOVA model as described in Section 9.2.1. Descriptive statistics and LS means for change from baseline to Week 28 in each of these hormone parameters will be presented by treatment group along with the LS-mean treatment difference, 95% confidence intervals, and p-value.

As an additional analysis, the change from baseline to Week 28 in mean morning salivary samples (average of 0600, 0800, +3 hours post-GC dose, and +6 hours post-GC dose) for each of the parameters will be analyzed using an ANCOVA model as described in Section 9.2.1. Descriptive statistics and LS means for change from baseline to Week 28 in each of these parameters will be presented by treatment group along with the LS-mean treatment difference, 95% confidence intervals, and p-value.

Mean ( $\pm$ SEM) values of salivary hormone parameters at each visit will be summarized in line graphs by treatment group. Pre-dose values and mean 24-hour values will be presented on separate plots. Similar graphs will be presented for the changes from baseline.

The relationship between salivary and serum values will be depicted graphically for androstenedione, testosterone, and cortisol. Scatterplots of salivary vs. timepoint-matched serum values will be generated by treatment group. The correlation coefficient, R, will be calculated and displayed in the scatterplots. A regression line will also be displayed on the scatterplots.

### 9.6.3. Metabolic Assessments (Fasting Lipids and HOMA-IR)

Metabolic assessments collected on this study include HOMA-IR and fasting lipids (total cholesterol, LDL, HDL, and triglycerides). The change from baseline to Week 28 for each of these parameters will be analyzed using an ANCOVA model as described in Section 9.2.1. Descriptive statistics and LS means for change from baseline to Week 28 for each of these parameters will be presented by treatment group along with the LS-mean treatment difference, 95% confidence intervals, and p-value.

#### 9.6.4. Testicular Adrenal Rest Tumors (TARTs)

For male subjects with TARTs, the length, width, and depth of each lesion will be measured and recorded on the eCRF. For the purpose of summarization and analysis, the volume of each lesion will be used to assess size (in cubic millimeters) at visits where the testicular ultrasound is performed. Volume will be calculated using the following formula: volume = length x width x depth x 0.5236. The volume of each testicle will be calculated using the same formula. Descriptive statistics will be used to summarize the total TART volume (calculated as the sum of the volume of each lesion across both testes) for each subject by treatment group and visit. Observed and change from baseline values will be included in the summary table. Note that only male subjects with TARTs at baseline will have a testicular ultrasound performed at Week 28.

Additionally, the total TART volume will be expressed as a percentage of the total testicular volume and calculated as the sum of the volume of each lesion across both testes divided by the total testicular volume across both testes for each subject. The total TART volume as a percentage of the total testicular volume will be summarized with descriptive statistics by treatment group and visit. Observed and change from baseline values will be included in the summary table.

Change from baseline to Week 28 in total TART volume as a percentage of total testicular volume in the subset of male subjects with TARTs at baseline will be analyzed using an ANCOVA model, as described in Section 9.2.1 (with the exception of sex as a stratification factor in the model). Descriptive statistics and LS means for change from baseline to Week 28 in total TART volume as a percentage of total testicular volume will be presented by treatment group along with the LS-mean treatment difference, 95% confidence intervals, and p-value.

The number and percentage of subjects with the presence of TARTs (Y/N), whether they are unilateral or bilateral, and the average number of TARTs per subject will be summarized with descriptive statistics by visit and treatment group. The number and percentage of TARTs with each shape (round; lobular; irregular), boundary (clear; indistinct), hypervascularity (Y/N), calcification (Y/N), and the echogenicity will be summarized with descriptive statistics by visit and treatment group.

A response assessment will be conducted at Week 28 for subjects with the presence of TARTs at baseline. Response categories and the criteria for each category are detailed in Table 7. The frequency and percentage of subjects meeting each classification at Week 28 (as compared to baseline) will be summarized by treatment group. Complete responders will also be analyzed using a CMH test as described in Section 9.2.2. The CMH test will compare treatment groups and will include the stratification factors used in the randomization (with the exception of sex). The p-value from the CMH analysis will also be displayed in a table. This analysis will be repeated with complete and partial responders pooled together.

#### Table 7: Response Categories

Response Category	Definition
Complete Response (CR)	Disappearance of all TARTs.

Response Category	Definition
Partial Response (PR)	$\geq$ 30% decrease in total TART volume compared with baseline
Progressive Disease (PD)	≥30% increase in total TART volume compared with baseline
Stable Disease (SD)	Neither CR, PR nor PD

### 9.6.5. Menstrual Regularity

Female subjects who have undergone menarche and are not on hormonal or intrauterine device contraceptives were asked to input the dates for which they were assessing their menstrual cycle as well as the amount of flow (light [spotting], medium [normal flow], heavy [heavy flow with flooding or clotting]). For the purposes of analysis, a menstrual cycle will be defined as two consecutive calendar days with any amount of flow. Menstrual cycle regularity is defined as a menstrual cycle every 21-35 days, translating to approximately 5 to 10 menstrual cycles from baseline to Week 28. As menstrual cycles can be irregular in the first year of menses, the following analysis will be restricted to female subjects in Tanner stages 4 and 5 only. The number and percentage of female subjects meeting the definition for regular menstrual cycle at Week 28 will be summarized by treatment group. This summary will be stratified based on menstrual cycle regularity at study entry (as collected on the "conditions of interest" eCRF, "irregular menstrual cycles" [yes or no]). This endpoint will be analyzed using a CMH test as described in Section 9.2.2. The CMH test will compare treatment groups and will include the stratification factors used in the randomization (with the exception of sex) as well as menstrual cycle regularity at study entry. The p-value from the CMH analysis will also be displayed in a table.

### 9.6.6. Growth

In subjects not at adult height (female subjects with the most recent prior bone age <14 years and males with the most recent prior bone age <16 years at study entry) and not on gonadotropin-releasing hormone agonist therapy, growth hormone therapy, or aromatase inhibitors at study entry, height SDS will be summarized with descriptive statistics by visit and treatment group.

The change from baseline to Week 28 in height SDS is an exploratory endpoint and will be analyzed using ANCOVA model as described in Section 9.2.1. Descriptive statistics and LS means for change from baseline to Week 28 in height SDS will be presented by treatment group along with the LS-mean treatment difference, 95% confidence intervals, and p-value.

### 9.6.7. Bayley-Pinneau Predicted Adult Height SDS

The change from baseline in Bayley-Pinneau predicted adult height SDS at Week 28 will be analyzed using an ANCOVA model, as described in Section 9.2.1. Bayley-Pinneau predicted adult height SDS will be determined at baseline and Week 28 using the height and bone age of the subject at these respective visits and compared against the boys and girls tables of predicted heights (Bayley and Pinneau, 1952). The Bayley-Pinneau predicted height for all subjects will be based on the "average" boys/girls tables with the exception of subjects who have an advanced or delayed bone age in excess of 1 year from the chronological age, in which case the "accelerated" or "retarded" predicted height tables will be used, respectively. Descriptive statistics and LS means for change from baseline to Week 28 in Bayley-Pinneau predicted adult height SDS will be presented by treatment group along with the LS-mean treatment difference, 95% confidence intervals, and p-value.

### 9.6.8. Hirsutism

Visual analog scales (VAS) were used to assess the subject's perception of severity of hirsutism in all female subjects, scored on a 100 mm visual analog scale, from 0 mm (no symptoms) to 100 mm (very severe symptoms). Observed and change from baseline values in VAS scores for hirsutism will be summarized descriptively by visit and treatment group.

The change from baseline to Week 28 in VAS score for hirsutism (female subjects only) will be analyzed using an ANCOVA model as described in Section 9.2.1 (with the exception of sex as a stratification factor in the model). Descriptive statistics and LS means for change from baseline to Week 28 in the VAS score for hirsutism will be presented by treatment group along with the LS-mean treatment difference, 95% confidence intervals, and p-value.

### 9.6.9. Acne

Visual analog scales (VAS) were used to assess the subject's perception of severity of acne in all subjects, scored on a 100 mm visual analog scale, from 0 mm (no symptoms) to 100 mm (very severe symptoms). Observed and change from baseline values in VAS scores for acne will be summarized descriptively by visit and treatment group for each sex as well as both sexes combined.

The change from baseline to Week 28 in VAS score for acne is an exploratory endpoint and will be analyzed using an ANCOVA model as described in Section 9.2.1. Descriptive statistics and LS means for change from baseline to Week 28 in the VAS score for acne will be presented by sex and treatment group along with the LS-mean treatment difference, 95% confidence intervals, and p-value.

### 9.6.10. Weight

Weight SDS will be summarized with descriptive statistics by visit and treatment group.

The change from baseline to Week 28 in weight SDS is an exploratory endpoint and will be analyzed using ANCOVA model as described in Section 9.2.1. Descriptive statistics and LS means for change from baseline to Week 28 in weight SDS will be presented by treatment group along with the LS-mean treatment difference, 95% confidence intervals, and p-value.

### 9.6.11. Glucocorticoid Dose Regimen

In subjects on hydrocortisone alone at baseline with a dosing frequency of more than once per day (eg, 5x/day, QID, TID, or BID), a responder is defined as a subject whose dose is reduced by at least one dosing instance per day at Week 28. For example, responders include subjects who reduce from QID to TID (or BID or QD), TID to BID (or QD), or BID to QD, from baseline to Week 28. The number and percentage of subjects meeting this responder definition at Week 28

will be summarized by treatment group. A shift table of hydrocortisone dosing frequency from baseline to Week 28 will also be presented. The rows of the shift table will reflect the dosing frequency at baseline and the columns will reflect the dosing frequency at Week 28. The number and percentage of subjects in each shift category will be displayed in the table; percentages will be based on the number of subjects included in the table.

In subjects on a prednisone or equivalent (eg, methylprednisolone or prednisolone) or a hydrocortisone + prednisone (or equivalent) regimen at baseline, a responder is defined as a subject who switches to a hydrocortisone alone regimen at Week 28 (ie, a subject who stops taking prednisone or equivalent prior to the Week 28 visit and is on a hydrocortisone-only regimen at Week 28). The number and percentage of subjects meeting this responder definition at Week 28 will be summarized by treatment group.

The achievement of response for hydrocortisone alone dosing frequency reduction and switching from prednisone regimen to hydrocortisone alone at Week 28 (as defined for each of the responder analyses described above) will be analyzed using a CMH test as described in section 9.2.2. The CMH test will compare treatment groups and will include stratification factors used in the randomization. Subjects who are missing Week 28 data will be omitted from the analysis.

### 9.7. Examination of Subgroups

The following subgroups have been pre-planned and will be used to examine consistency of effect for the primary efficacy endpoint:

- Region (OUS versus US)
- Sex (male versus female; based on eCRF)
- BMI (<  $85^{\text{th}}$  percentile versus  $\geq 85^{\text{th}}$  percentile)
- Race (White, Black or African American, Asian, Native Hawaiian or Other Pacific Islander, American Indian or Alaska Native)
- Pubertal stage (Tanner stages [breast or testicular] 1, 2 versus Tanner stages 3, 4, 5; based on eCRF)
- Age (< 12 years versus 12 17 years)
- Baseline and rost endione (midpoint of normal range to < ULN versus  $\ge$  ULN)

If any of these categories are sparse in number of subjects (eg, <15), the categories with the fewest number of subjects may be collapsed until there are at least 15 subjects or the subgroup analysis may be omitted entirely. The decision to omit a subgroup analysis will be justified in the CSR. Each subgroup will be analyzed separately using an ANCOVA model that is similar to the model used in the primary analysis of the primary endpoint (as described in Section 9.2.1), with the addition of the subgroup variable added as a main effect term and an interaction term between treatment group and the subgroup variable. Note that for the sex and pubertal stage subgroups, the values reported on the eCRF will be used in the model instead of the values reported as stratification factors in the IRT. Nominal two-sided p-values for comparing treatment groups and the associated 95% confidence intervals will be reported in summary tables and a

forest plot, with p-values for the interaction term between treatment groups and subgroup variables presented.

## **10. EFFICACY – OL PERIOD**

The efficacy endpoints and planned analysis methods for the OL period are described below. The OL period safety analysis set will be used for all efficacy analyses and descriptive statistics in the OL period. Unless otherwise noted, the summaries described below will follow the treatment group and baseline definitions defined for the OL period (as described in Section 6). Missing data will not be imputed for any of the following analyses and all summary displays will start with Week 32 as the first postbaseline visit, unless otherwise specified.

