## 9.11. Discontinuation of Study Drug and Subject Withdrawal

Parent/legal guardian (or the subject, if the subject has reached the age of majority) can discontinue study drug or withdraw their consent for the subject to participate in the study at any time during the core study or during the OLE. The investigator must discontinue study drug dosing or withdraw any subject from the study if a subject requests study drug dosing to be discontinued or to be withdrawn from the study, respectively. All subjects prematurely discontinuing study drug dosing prior to Week 52 should continue study participation to be followed for safety and efficacy outcomes up to the Week 52 visit; subjects who discontinue study drug dosing during the OLE will be withdrawn. Subjects who discontinue study drug prior to Week 52 are ineligible for the OLE.

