#### 9.11.1. Discontinuation of Study Drug Dosing

If a subject prematurely discontinues study drug dosing, the investigator will record the reason for discontinuation on the relevant eCRF. Subjects who prematurely discontinue study drug dosing prior to Week 52 will not be automatically withdrawn from the study and should continue participation in the study through Week 52. Data for any outcome measures, particularly the primary and secondary endpoints, as well as safety follow-up, are important to collect through the Week 52 visit. A PK sample should be collected within approximately 4 weeks of the last study drug dose, after which additional PK sampling would not be required. Subjects should be followed for safety evaluations (which can be done at scheduled visits) for at least 4 weeks after the last dose of study drug. If medically indicated, treatment with medication listed under Section 9.10.1 is no longer prohibited after study drug discontinuation. Following discontinuation of study drug, the subject's glucocorticoid dose should be monitored and adjusted to achieve control of androgen levels as appropriate for that subject. Palatability of the study drug at the early termination visit is not required if the subject has discontinued study drug.

Reasons for discontinuation of study drug dosing are:

- Withdrawal by subject
- Death
- Lost to follow-up
- Site termination by the Sponsor
- Study termination by the Sponsor
- AE
- Pregnancy
- Lack of efficacy
- Protocol deviation
- Protocol-specified withdrawal criterion met
- Investigator decision
- Sponsor decision

The investigator must discontinue study drug dosing if the subject experiences any of the following:

- QTcF value >500 msec (cardiologist verified) on any ECG tracing.
- If the subject exhibits suicidal behavior, or suicidal ideation of type 4 (active suicidal ideation with some intent to act, without specific plan) or type 5 (active suicidal ideation with specific plan and intent) based on the C-SSRS.

It is crucial to obtain follow-up data for any subject who discontinues study drug dosing because of an AE, abnormal laboratory test, vital sign measurement, physical examination, or ECG finding. In any case, every effort must be made to undertake safety follow-up procedures.

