#### 13.6.1.4. Secondary Endpoints

Secondary endpoints will be compared by treatment group and will not be adjusted for multiplicity. Analysis methods for these endpoints will be described in the SAP. These analyses will be performed using observed data in the FAS.

The secondary endpoints include:

- The achievement of a reduction in glucocorticoid daily dose to physiologic levels (≤11 mg/m²/day in hydrocortisone dose equivalent adjusted for BSA) at Week 28 while serum A4 is ≤120% of the baseline value or ≤ULN for sex and either age (for Tanner stage 1) or pubertal stage (for Tanner stages 2 to 5)
- Change from baseline in body mass index SDS at Week 28
- Change from baseline in mean 24-hour salivary 17-OHP at Week 28
- Acceptability and palatability of the study drug at Week 4

In the subgroup of subjects not at adult height, secondary endpoints will also include:

- Ratio of the change in bone age from baseline to Week 28 to the change in chronologic age from baseline to Week 28
- Change from baseline in Bayley-Pinneau predicted adult height SDS at Week 52

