## 6.2. Analysis Sets

#### Table 1: Definitions of Analysis Sets

Analysis Set	Description
Full Analysis Set	The full analysis set (FAS) will include all randomized subjects. Subjects will be analyzed according to their randomized treatment group, regardless of adherence to study drug administration.
DB Period Safety Analysis Set	The DB period safety analysis set (SAS) will include all randomized subjects who take at least 1 dose of study drug in the double-blind period. Subjects will be analyzed according to their randomized treatment group, unless they receive the incorrect study drug for the entire double-blind treatment duration.
OL Period Safety Analysis Set	The OL period safety analysis set (SAS) will include all subjects who take at least 1 dose of active study drug (crinecerfont) during the open-label period.
PK Analysis Set	The PK analysis set (PKAS) will include all subjects randomized to crinecerfont who take at least 1 dose of study drug and have at least one post-dose PK concentration.

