## 9. EFFICACY – DB PERIOD

The efficacy endpoints and planned analysis methods for the DB period are described below. Unless otherwise specified, the FAS will be used for all efficacy analyses.

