## 10.6. Bayley-Pinneau Predicted Adult Height SDS

The change from baseline in Bayley-Pinneau predicted adult height SDS at Week 52 is a secondary endpoint, which will be analyzed using an ANCOVA model, as described in Section 9.2.1. Bayley-Pinneau predicted adult height SDS will be determined at baseline and Week 52 using the height and bone age of the subject at these respective visits as described in Section 9.6.7.

Descriptive statistics and LS means for change from baseline to Week 52 in Bayley-Pinneau predicted adult height SDS will be presented by treatment group (from the double-blind period) along with the LS-mean treatment difference, 95% confidence intervals, and p-value.

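### The Week 52 predicted-adult-height ANCOVA compares the randomized groups in a set that requires an open-label dose, where the protocol specifies the FAS; the SAP does not declare the change

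*SAP*

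**What the plan says.** Protocol 13.6.1.4 lists the Week 52 change in Bayley-Pinneau predicted adult height SDS, in children not at adult height, among the secondary endpoints. It fixes the population for that list: "These analyses will be performed using observed data in the FAS". Protocol Table 17 defines the FAS as everyone randomized, grouped as randomized, whatever their adherence.

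SAP 4.5 places the endpoint in the open-label period. SAP Section 10 then sets the population for that period: "The OL period safety analysis set will be used for all efficacy analyses and descriptive statistics in the OL period". Table 1 of the SAP says this set "will include all subjects who take at least 1 dose of active study drug (crinecerfont) during the open-label period". SAP 10.6 names no other set, but reports the comparison by original assignment: results "will be presented by treatment group (from the double-blind period) along with the LS-mean treatment difference, 95% confidence intervals, and p-value".

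On children who stop drug before Week 52, Protocol 9.11 says they "should continue study participation to be followed for safety and efficacy outcomes up to the Week 52 visit". Protocol 9.11.1 adds that they "will not be automatically withdrawn from the study and should continue participation in the study through Week 52". SAP Section 14 presents its list of departures from the protocol's analysis as complete.

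**The concern.** Section 10.6 is not an open-label summary. It is the only between-group test in SAP Section 10, and the groups compared are the randomized ones. Membership of its analysis set depends on taking a dose at or after Week 28. The reasons for stopping drug listed in Protocol 9.11.1 include adverse events and lack of efficacy, so the children left out need not resemble those kept. The FAS exists to protect a randomized contrast from this kind of selection, and the protocol chose it for this endpoint. A reader of the study report would see a protocol secondary endpoint tested in a different population, with nothing in Section 14 to say so.

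**Working it through.** The plan gives no figure for this analysis, so there is none to reproduce. Its power statement (Protocol 13.4, SAP 3.3) concerns Week 4 androstenedione and is not at issue.

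**Does the text exclude these children?**

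- Population: observed FAS data in Protocol 13.6.1.4; the OL period safety set in SAP 10. The SAP's own FAS default sits in Section 9, which covers the double-blind period only.
- Exceptions: the sentence in SAP 10 that allows for exceptions concerns treatment-group and baseline definitions. The analysis-set sentence has none, and 10.6 changes only the grouping.
- Can such a child have data? Protocol Table 7 schedules height and bone age at Week 52, and Protocol 9.11 asks for efficacy follow-up to that visit. A child who stopped in the double-blind period and stayed on study can therefore have both baseline and Week 52 values, and would be in the FAS but not in the open-label set.
- Disclosure: SAP 14 lists two changes, both to the safety set: removal of the postbaseline-data condition, and the split into two period sets. Neither says that the open-label set replaces the FAS for an efficacy endpoint.

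**How many children?** The documents give no discontinuation rate. Assume that 0% to 15% of the 81 randomized take no open-label dose and that 50% to 100% of these have Week 52 data. At 5%, 0.05 × 81 = 4.05, so 2 to 4 children; at 15%, 0.15 × 81 = 12.15, so 6 to 12. These are upper bounds, because only children not at adult height count.

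**How large a shift?** Let n be the children in an arm with observed values, k those excluded, and g the retained mean minus the excluded mean, in SDs of the change. Exclusion moves the arm mean by (k/n) × g, so the crinecerfont-minus-placebo difference moves by (k_c/n_c) × g_c − (k_p/n_p) × g_p. The unadjusted SE is sqrt(1/n_c + 1/n_p): sqrt(1/24 + 1/12) = 0.354 and sqrt(1/54 + 1/27) = 0.236. The arm sizes (24/12 up to the full 54/27), k and g (0.3 to 1.0, excluded children doing worse) are all assumptions.

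| Excluded | g | Shift (SD) | Shift / SE |
|---|---|---|---|
| none | any | 0 | 0 |
| 1 of 54 crinecerfont | 0.3 | +0.006 | 0.006/0.236 = +0.02 |
| 1 of 24 crinecerfont | 1.0 | +0.042 | 0.042/0.354 = +0.12 |
| 3 of 24 crinecerfont | 1.0 | +0.125 | 0.125/0.354 = +0.35 |
| 1 of 27 placebo | 0.3 | −0.011 | −0.011/0.236 = −0.05 |
| 1 of 12 placebo | 1.0 | −0.083 | −0.083/0.354 = −0.24 |
| 2 of 12 placebo | 1.0 | −0.167 | −0.167/0.354 = −0.47 |
| 2 of 24 and 1 of 12 | 0.5 each | 0.042 − 0.042 = 0 | 0 |
| 8 of 54 crinecerfont (15% of arm) | 1.0 | +0.148 | 0.148/0.236 = +0.63 |
| 4 of 27 placebo (15% of arm) | 1.0 | −0.148 | −0.148/0.236 = −0.63 |

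If excluded children do better than those kept, every sign reverses.

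**The case against.** The protocol leaves analysis methods for secondary endpoints and open-label data to the SAP, and Protocol 13.5 allows the SAP to add analysis sets. That is true, and a declared change would be legitimate. But the FAS sentence in 13.6.1.4 is specific. Adding a set does not replace the one named there, and the change was not declared.

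The FAS analysis would itself be observed-case, so it also conditions on something after randomization, namely having a Week 52 value. This stands: restoring the FAS reduces the selection but does not remove it.

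A reader might infer that the SAP contradicts itself. For the double-blind period it says "Unless otherwise specified, the FAS will be used for all efficacy analyses", and at Week 28 "The change from baseline in Bayley-Pinneau predicted adult height SDS at Week 28 will be analyzed using an ANCOVA model". Table 5 also gives a Week 52 window (Day 337 to 378) to children with no open-label dose date. The documents do not support that inference. The SAP assigns sets by period, and the contrasts differ: crinecerfont against placebo at Week 28, but 52 weeks of crinecerfont against 28 of placebo followed by 24 of crinecerfont at Week 52. Table 5 also serves children who stop during the open-label period, and they are in the open-label set. The case rests on the protocol sentence, not on these comparisons.

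It would also be too strong to say that follow-up to Week 52 is mandatory: the protocol says that these children should continue.

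**Conclusion.** The point holds as a departure from the protocol's stated analysis set, undeclared in Section 14, for a comparison of randomized groups. It affects only children not at adult height who took no open-label dose and have observed Week 52 height and bone age. Those who stop after at least one open-label dose stay in the set, and those without a Week 52 value are absent either way.

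The size is not known. The documents give no discontinuation rate, no SD for this endpoint and no count of children not at adult height. In the assumed scenarios the shift runs from zero to about 0.6 SE in either direction, the largest needing 15% of one arm excluded, none of the other, and a gap of a full SD. A reader might infer that the choice favours crinecerfont or threatens the trial's conclusions. Neither follows: the direction is unknown, and Protocol 13.6.1.1 keeps this p-value nominal and outside the fixed sequence. The change is still worth making, because it is cheap and removes an avoidable selection.

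**What to change.** In SAP 10 and 10.6, state: *The Week 52 Bayley-Pinneau predicted adult height SDS ANCOVA uses all FAS subjects not at adult height with an observed Week 52 value, by randomized group, regardless of study drug discontinuation or open-label entry. The number with a missing Week 52 value will be reported by randomized group.* Keep the OL period safety set for a supplementary version and for the descriptive tables. This restores the protocol's set, so Section 14 needs no entry. If the open-label set is kept as the main analysis instead, Section 14 must list and justify it; restoring the FAS is the better course.

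One optional clarification concerns Table 6, where both bone-age windows end 28 days after a first open-label or OLE dose that some children never take. If a limit is added for them, it should keep Table 6's wider window, for example target day + 28 (196 + 28 = Day 224; 364 + 28 = Day 392), applied to a row only when that row's own dose date is absent. Table 5's limits (Day 210 and Day 378) would be too tight. Protocol 9.3.4 allows a repeat film within 2 weeks of the visit, so a visit at Day 364 + 7 = 371 could have a valid film at Day 371 + 14 = 385.

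The cost is two sentences, one count by arm and, if wanted, one table note. No new procedures are needed.
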